The U.S. and Europe populations are getting older. For instance, in the United States, the population aged 80-84 years increased by 16.1%, and those aged 85-89 years increased by 29.8% from 2000 to 2010¹⁸. Although not excluded from the large CRT randomized trials^{9, 10}, older patients (≥ 75 years) have been largely underrepresented in these trials but still receive up to 40% of all CRT-D's in the United States^{19,38}. Moreover, older patients have a higher risk of death than younger patients based on competing causes of death and comorbid conditions, thus stirring controversy regarding the role of defibrillator therapy in the elderly²⁰⁻²⁴. In addition, data from large CRT-D registries show that the odds of receiving appropriate defibrillator shocks decrease significantly with every decade of age²⁵.

Potential Impact

A large, randomized, non-inferiority trial comparing mortality and QOL in older HF patients receiving CRT-P versus CRT-D therapy addresses a critical clinical practice area. Uncertainty about the comparative outcomes of older patients with these two therapies leads to suboptimal and costly management of HF: Older CRT recipients often receive the larger and more expensive CRT-D device that can deliver painful shocks, in the absence of any proof for incremental survival benefit with CRT-D over CRT-P. The pilot randomized trial of this proposal (Aim 1) will be essential to the design of a large pivotal trial. This project will also have significant scientific impact because it will evaluate the clinical and demographic predictors of choosing CRT-P or CRT-D therapy as well as patients' change in their satisfaction with their decision 6 months after enrollment. The results of this research will ultimately effect clinical change in the management of elderly CRT recipients driven by changes to the CRT published guidelines. This research is likely to impact clinical practice and will be important to many stakeholders, including elderly patients and their families, physicians, hospitals, and third party payers, especially Medicare.

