In addition, patients enrolled in the observational cohort will be asked about their decision to receive a CRT-P or CRT-D device and will be probed for the reason (s) behind their decision and their answers will be recorded. The actual type of device implanted (CRT-P versus CRT-D) will be ascertained at the time of the implantation procedure. At baseline and at the 6-month research call, they will be assessed for their level of satisfaction with their decision about device therapy (CRT-P or CRT-D) using the Satisfaction with Decision Scale³²⁻³⁴ (Appendix 3), which assigns a score of 1 to 5 to the answer of each of 6 questions pertaining to the patient's level of satisfaction with their medical decision (lowest satisfaction score is 6 and highest is 30).

Table 2. Schedule of Events	Enrollment visit	Device implant	30-day phone call	3-month phone call	6-month visit or phone call	Every 6 months phone call	End of Study
Demographic Information	X						
Baseline Clinical Characteristics	X						
Medications	X				X	X	X
Procedural Complications		X	X				
Clinical Events (survival, hospitalizations, arrhythmias)		X	X	X	X	X	X
The Satisfaction with Decision Scale	X				X		
Quality of Life Questionnaires	X				X		
Device complications		X		X	X	X	X
Device Interrogation		X			X	X	X
Economic Data							X

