All patients who do not enroll in the trial, but consent to be followed, will be enrolled in a parallel observational cohort. Patients’ clinical and demographic characteristics will be examined and compared between CRT-P and CRT-D recipients using t-tests, Wilcoxon rank-sum tests, chi-squared tests, or Fisher’s Exact tests, as appropriate. Patient satisfaction among CRT-P vs. CRT-D recipients will be assessed at baseline and 6 months after enrollment using the Satisfaction with Decision Scale. The scores will be presented as mean (SD) and tested using a 2-sample t-test (or Wilcoxon test if the data are non-normally distributed). Deceased patients will be included in the analysis (assigned the lowest possible satisfaction score of 6) to avoid survival bias in the event of differential mortality in CRT-P vs. CRT-D. Cost of care will also be presented as mean (SD) and compared between the two cohorts using a 2-sample t-test (or Wilcoxon test if the data are non-normally distributed). Multivariate modeling with adjustment for selected patient factors will be considered if there are differences in CRT-P vs. CRT-D patients on key demographics, but the power to test this difference while accounting for multiple confounders may be limited.

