9.2 SAMPLE SIZE

Randomized Aim

It will be of interest to estimate the recruitment success rate and the retention rate in this population, as that will be useful knowledge for designing a pivotal non-inferiority trial. The proposed sample size of 50 patients guarantees a maximum sample standard deviation = $\sqrt{(.5*(1-.5)/50)} = 7\%$, meaning that a 95% confidence interval will have a maximum margin of error $\pm 13\%$ in estimating true retention rate. However, this margin-of-error may be lower (the further the sample retention is from 50%). For example, if 40/50=80% participants enrolled complete at least the 6-month visit, a 95% CI estimating the true 6-month retention in this population would range from 68.9-91.1%, information that can be used to guide recruitment estimates for the large scale trial. The recruitment success rate can be estimated with even more precision, as there will be a larger N approached than N enrolled (and thus a smaller standard deviation of the sample proportion).

Observational Aim

It is anticipated based on the physician and patient surveys that approximately 40% of patients offered the opportunity to enroll in the pilot randomized controlled trial of Aim 1 will do so. Therefore, 125 patients will need to be screened to enroll 50 in the pilot randomized trial. It is assumed that 80% of those who decline participation in Aim 1 will agree to be followed in the observational cohort, the cohort will consist of 60 non-randomized patients. A comparison will be scored on the Satisfaction with Decision Scale using a t-test (or Wilcoxon rank-sum test, if non-normally distributed). Assuming roughly equal numbers select CRT-D vs. CRT-P, enrollment of 60 cohort participants will have 80% power to detect a difference in Satisfaction with Decision scores if one treatment group's average score is at least 0.75 standard deviations higher than the other group.

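### Section 2.1 says change in decision satisfaction will be evaluated, but section 9.1 only compares scores between devices, so change is not estimated and baseline is not linked to the 6-month score

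*Combined protocol and SAP*

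**What the plan says.** Under Potential Impact, section 2.1 lists among the things the project will evaluate the patients' "change in their satisfaction with their decision 6 months after enrollment".

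The data for this are scheduled. Section 6 (Observational Aim) says: "At baseline and at the 6-month research call, they will be assessed for their level of satisfaction with their decision about device therapy". Table 2 marks the scale at enrollment and at 6 months. It has six items scored 1 to 5, so totals run from 6 to 30.

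The analysis is in section 9.1, Observational Aim: "Patient satisfaction among CRT-P vs. CRT-D recipients will be assessed at baseline and 6 months after enrollment using the Satisfaction with Decision Scale". Then: "The scores will be presented as mean (SD) and tested using a 2-sample t-test", with a Wilcoxon test as the alternative for non-normal data. Deceased patients stay in the analysis, "assigned the lowest possible satisfaction score of 6", to guard against survival bias. On adjustment: "Multivariate modeling with adjustment for selected patient factors will be considered if there are differences in CRT-P vs. CRT-D patients on key demographics". The baseline satisfaction score is not named as a covariate.

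Section 9.2 says that "enrollment of 60 cohort participants will have 80% power to detect a difference in Satisfaction with Decision scores" of at least 0.75 SD between the groups' average scores, with roughly equal numbers choosing each device. It does not say at which time point.

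**The concern.** A 2-sample test compares different people. It cannot show whether satisfaction rose or fell among those who chose a given device. That is a within-patient quantity, and its standard error needs the pairing.

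A reader could subtract the reported baseline mean from the reported 6-month mean, but would have no valid standard error. The two means would also differ in membership by any patients lost to follow-up for reasons other than death (section 5.5).

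The device groups in Aim 2 are self-selected, so their satisfaction may already differ at enrollment. An unadjusted 6-month contrast then mixes that starting difference with whatever arose after living with the device. Satisfaction is the only outcome on which section 9.2 sizes the observational cohort, so this limits what the cohort can say about it.

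**Working it through.** **Inputs from the documents.** 60 patients, about 30 per device, 0.75 SD, 80% power (9.2); scale range 6 to 30 (6); deaths scored 6 (9.1).

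**Assumptions.** Two-sided alpha 0.05, because none is stated for this comparison. Baseline to 6-month correlation r = 0.3, 0.5 or 0.7, because none is given. Equal SDs at both times, no losses, and no extra variance from the death score.

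**1. The plan's own figures.**
- Cohort size: 50/0.40 = 125 approached; (125 − 50) × 0.80 = 60.
- Power: two-sample t-test, 30 per group, 0.75 SD gives 81.5% (noncentral t).
- With the Wilcoxon test at relative efficiency 0.955: 79.6%.
- Difference detectable at exactly 80% power: 0.736 SD.

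The stated 80% therefore reproduces as a comparison of scores between two independent groups. It uses neither change nor baseline adjustment.

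**2. Precision of the within-device change.** Half-width of the paired 95% CI = t(0.975, 29) × √(2(1 − r)/30), with t = 2.045.
- r = 0.3: 2.045 × √(1.4/30) = 0.44 SD
- r = 0.5: 2.045 × √(1.0/30) = 0.37 SD
- r = 0.7: 2.045 × √(0.6/30) = 0.29 SD

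**3. Adjusting the 6-month contrast for baseline.** The residual SD is √(1 − r²) times the raw SD (the one degree of freedom lost is ignored). Detectable difference = 0.736 × √(1 − r²); power is for a true 0.75 SD difference.

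| r | detectable at 80% power | power, adjusted | power, raw change score |
|---|---|---|---|
| 0.3 | 0.736 × 0.954 = 0.70 SD | 84.9% | 67.5% |
| 0.5 | 0.736 × 0.866 = 0.64 SD | 91.0% | 81.5% |
| 0.7 | 0.736 × 0.714 = 0.53 SD | 97.9% | 95.8% |

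The unadjusted test has 81.5% throughout. A 2-sample test on raw change scores beats it only if r exceeds 0.5, so it is not the better main contrast.

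**4. Carry-over.** Suppose the groups differ by d at baseline, the device has no effect, and the 6-month score follows the baseline score by the same line in both groups. The unadjusted 6-month contrast is then expected to be r × d: 30%, 50% or 70% of the starting difference. The change-score contrast is expected to be −(1 − r) × d. The adjusted contrast is expected to be zero. The three can disagree, so the main one must be named in advance.

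**5. Deaths.** A patient who starts at 30 and dies contributes 6 − 30 = −24 to the change. Among 30 patients, that one death moves the mean change by 24/30 = 0.8 points. The death rule therefore has to be explicit for change, and a survivors-only figure is needed beside it.

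**The case against.** The strongest reply is that change is mentioned once, in background. The objectives (section 3) and endpoints (section 4.2) do not list satisfaction. Sections 2.2, 4.1 and 6 speak of measuring it at baseline and 6 months, and section 9.1 follows them. Section 9.3 gives the main purpose of Aim 2 as learning who refuses randomization and why. This stands, and it keeps the point modest. But section 2.1 says plainly that the change will be evaluated. If that is not intended, the sentence there should be altered.

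Baseline adjustment is also a choice. With self-selected groups, adjusted and change-score results can differ. Section 5.3 allows enrollment up to fourteen days after the procedure, so some baseline scores may follow the implant. Both points stand and are met in the fix.

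A reader might infer more than the documents support:
- *Two tests inflate the type I error.* Section 9.1 does not say that a formal test is done at each time, section 9.2 describes one comparison, and no alpha is stated.
- *The baseline scores go unused.* They are collected and summarised; they are just not linked to the same patient's later score. If the groups are also compared at baseline, a starting difference would be visible, though not removed from the 6-month contrast.
- *Deaths drop out of the 6-month mean.* They are kept, with a score of 6. Only other losses change who is counted.
- *The study asks about decision regret.* The documents do not name it as a question.

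**Conclusion.** The mismatch is real: section 2.1 announces an evaluation of change, the paired scores are collected, and section 9.1 contains no analysis that estimates it. This does not depend on any assumed figure.

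The size of the gain from baseline adjustment does. With 30 per device, two-sided 0.05 and r of 0.3, 0.5 or 0.7, the difference detectable at 80% power falls from about 0.74 SD to about 0.70, 0.64 or 0.53 SD. At r = 0.3 the gain is small. Losses, or extra spread from the death score, would make all these figures less favourable, including the half-widths for change.

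The sample-size statement is not wrong, and nothing here calls for more patients. The change is worth making because it makes the analysis match the stated intention using data already scheduled.

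**What to change.** Add to section 9.1, Observational Aim, wording such as:

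> The main device contrast is the difference in satisfaction score at 6 months between CRT-P and CRT-D recipients, estimated with the baseline score as covariate. The mean within-patient change from baseline to 6 months is reported for each device with a paired 95% confidence interval and is descriptive. Patients who have died are given a 6-month score of 6 in both analyses. The change among survivors is given as a companion analysis, with deaths per device reported beside it. The baseline comparison between devices is descriptive. The number of baseline scores obtained after implant is reported for each device.

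In section 9.2, state that the 80% power refers to the 6-month comparison.

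The planned unadjusted 2-sample test, or its Wilcoxon alternative, can remain as a sensitivity analysis.

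The cost is a few sentences in two sections and one extra count. Both scores are already in Table 2, and no patient or visit is added. The price is that adjusted and change results may point different ways if the groups start apart, which is why the main contrast is fixed in advance.

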9.2 SAMPLE SIZE

Randomized Aim

It will be of interest to estimate the recruitment success rate and the retention rate in this population, as that will be useful knowledge for designing a pivotal non-inferiority trial. The proposed sample size of 50 patients guarantees a maximum sample standard deviation = $\sqrt{(.5*(1-.5)/50)} = 7\%$, meaning that a 95% confidence interval will have a maximum margin of error $\pm 13\%$ in estimating true retention rate. However, this margin-of-error may be lower (the further the sample retention is from 50%). For example, if 40/50=80% participants enrolled complete at least the 6-month visit, a 95% CI estimating the true 6-month retention in this population would range from 68.9-91.1%, information that can be used to guide recruitment estimates for the large scale trial. The recruitment success rate can be estimated with even more precision, as there will be a larger N approached than N enrolled (and thus a smaller standard deviation of the sample proportion).

Observational Aim

It is anticipated based on the physician and patient surveys that approximately 40% of patients offered the opportunity to enroll in the pilot randomized controlled trial of Aim 1 will do so. Therefore, 125 patients will need to be screened to enroll 50 in the pilot randomized trial. It is assumed that 80% of those who decline participation in Aim 1 will agree to be followed in the observational cohort, the cohort will consist of 60 non-randomized patients. A comparison will be scored on the Satisfaction with Decision Scale using a t-test (or Wilcoxon rank-sum test, if non-normally distributed). Assuming roughly equal numbers select CRT-D vs. CRT-P, enrollment of 60 cohort participants will have 80% power to detect a difference in Satisfaction with Decision scores if one treatment group's average score is at least 0.75 standard deviations higher than the other group.

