9 STATISTICAL CONSIDERATIONS

9.1 STATISTICAL AND ANALYTICAL PLANS

Randomized Aim

Descriptive patient characteristics will be presented as mean (SD) for continuous variables and n (%) for categorical variables. Baseline comparisons of patients assigned to CRT-P vs. CRT-D will be performed using t-tests for continuous variables (Wilcoxon rank-sum test if non-normally distributed) and chi-squared tests for categorical variables (Fisher’s Exact Test in case of small sample sizes within cells) to confirm that the randomized treatment arms are balanced in key demographics and potential confounders. The proportion of patients experiencing major/minor procedural complications within 30 days will be reported as n (%) within each treatment arm. These complication rates will be ascertained through review of pertinent medical records following the device implantation. Mortality [as n (%)] and the 6-month QOL outcomes [as mean (SD)] within each treatment arm will be reported as well. Cost of care for the index hospitalization for CRT device implantation and for the follow-up period will be measured at the conclusion of the study and compared between the 2 cohorts using a 2-sample t-test (or Wilcoxon test if the data are non-normally distributed). Retention will be presented as n (%) completing at least 6-month of follow-up. In addition to the retention, in order to document the recruitment success, we will report the number of patients approached in order to successfully enroll n=50 patients, which will be useful information in planning a large scale trial.

Observational Aim

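### Section 9.2 gives a maximum 95% margin of error of ±13% for retention at n = 50, but its own formula gives ±13.9%

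*Combined protocol and SAP*

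**What the plan says.** Section 9.2 (Sample Size, Randomized Aim) justifies 50 patients by precision. "The proposed sample size of 50 patients guarantees a maximum sample standard deviation", it says, and it evaluates the square root of 0.5 × (1 − 0.5)/50 as 7%. From this it draws the conclusion "meaning that a 95% confidence interval will have a maximum margin of error" of ±13% for the true retention rate. It then notes that the margin can be smaller when retention is further from 50%, and illustrates this with 40 of 50 patients completing the 6-month visit: "a 95% CI estimating the true 6-month retention in this population would range from 68.9-91.1" percent.

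Section 9.1 (Randomized Aim) defines what will be reported: "Retention will be presented as n (%) completing at least 6-month of follow-up". No other section repeats or corrects the ±13%.

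**The concern.** A maximum margin is an upper bound: whatever retention turns out to be, the 95% interval should be no wider. The paragraph prints everything needed to check the bound, and the bound does not follow from those inputs. The error is in the optimistic direction.

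Retaining patients is part of the primary objective (Précis and section 3), and section 4.2.1 names retention among the feasibility elements the trial is to assess. Section 9.2 says the estimates are meant to help design the pivotal non-inferiority trial. This sentence is the only general statement of how precisely 50 patients will estimate retention, so a reader planning from it would take the worst-case precision to be slightly better than it is.

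**Working it through.** **Inputs, all from section 9.2:** n = 50; worst-case proportion p = 0.5; confidence level 95%. The section does not say whether the interval is two-sided, but a symmetric ± margin and the worked example both imply that it is, so z = 1.96.

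**Step 1. The plan's standard deviation.** √(0.5 × 0.5/50) = 0.0707, or 7.07%. The stated 7% reproduces.

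**Step 2. The plan's worked example.** For 40/50, the margin is 1.96 × √(0.8 × 0.2/50) = 0.1109. The interval is 80% ± 11.1 points, or 68.9% to 91.1%. This reproduces exactly and identifies the method as the normal approximation with 1.96. Other methods give different limits for 40/50: Wilson 67.0% to 88.8%, exact (Clopper-Pearson) 66.3% to 90.0%.

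**Step 3. The maximum margin by that method.**

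- Unrounded standard deviation: 1.96 × 0.0707 = 0.1386, or 13.9%.
- Rounded standard deviation: 1.96 × 0.07 = 0.1372, or 13.7%.

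Both round to 14%. The ±13% does not reproduce.

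**Step 4. Whether another method would give 13%.** Half-widths at 25/50:

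| Method | Half-width |
|---|---|
| Normal approximation, z = 1.96 | 13.86% |
| Same, multiplier 2 | 14.14% |
| Same, t with 49 degrees of freedom | 14.21% |
| Same, continuity-corrected | 14.86% |
| Same, one-sided z = 1.645 | 11.63% |
| Exact (Clopper-Pearson) | 14.47% |
| Jeffreys | 13.53% |
| Wilson | 13.36% |
| Agresti-Coull | 13.36% |

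Only Wilson and Agresti-Coull would round to 13%. The paragraph uses neither: it derives the margin from the simple standard deviation, and its example is the normal-approximation interval.

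**Step 5. Size of the discrepancy.**

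- Understatement: 13.86 − 13 = 0.86, about 0.9 percentage point.
- Confidence level at which a literal ±13% would hold when retention is 50%: z = 0.13/0.0707 = 1.84, a two-sided level of 93.4%.
- Sample size for a true 95% maximum of ±13%: 0.25 × (1.96/0.13)² = 56.8, so 57 patients. This only shows the scale; more patients are not needed.
- Observed counts at which 13% is exceeded: 1.96 × √(p(1 − p)/50) is 13.1% at 33/50 and 12.9% at 34/50. By symmetry the bound fails from 17/50 to 33/50, that is, for observed retention of 34% to 66%.

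**The case against.** The best case on the other side accepts the arithmetic and disputes its weight. The number 50 was not solved from ±13%. Section 9.1 reports retention only as a count and percentage, so the figure feeds no planned output. The bound fails only where the plan does not expect to be: its one scenario is 80% retention, and if that is the true rate, the binomial probability of observing 17 to 33 retained out of 50 is 1.4%. At 85% it is below 0.1%. It rises to 32% at a true rate of 70%, which the plan does not put forward. The paragraph also warns that the margin depends on the observed rate and follows with a correct interval at 80%.

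All of that stands, and it makes the consequence small. It does not make the sentence right, because the sentence states a maximum and the maximum is wrong.

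A second objection also stands: the plan does not show where 13 came from. Truncating 13.7 or 13.9 would produce it with the same 1.96 as the example, so one cannot conclude that a different multiplier was used. Likewise, the 93.4% describes what a literal ±13% would mean and does not show that such an interval was intended.

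**Conclusion.** The concern holds. Under section 9.2's own formula, sample size and confidence level, the maximum margin is ±13.9%, not ±13%. The understatement is about 0.9 point and cannot be explained by rounding. The conclusion assumes a two-sided 95% interval by the normal approximation, which the 40/50 example confirms.

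The correction should be made because this is the only general precision bound for part of the primary objective. The error does not affect the adequacy of the trial, any planned analysis, or the interval quoted at 80% retention.

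**What to change.** In section 9.2, Randomized Aim, replace ±13% with ±14% (13.9%). Keep n = 50 and leave the 40/50 example alone. The cost is one number in one sentence, with no extra patients and no change to any analysis.

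A separate, optional improvement that is not part of the correction: section 9.1 could add a 95% interval to the reported retention and name its method. At n = 50 the normal-approximation interval covers 93.8% of the time when true retention is 80%, but 87.9% when it is 90%; Wilson covers 95.1% and 97.0%. The normal-approximation upper limit also passes 100% for 47 to 49 retained of 50 (100.6% at 47). If another method is adopted, section 9.2 should follow it throughout:

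- Wilson: example 67.0% to 88.8%, maximum half-width 13.4%.
- Exact: example 66.3% to 90.0%, maximum half-width 14.5%.

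This would add one sentence to section 9.1 and change the matching figures in section 9.2.
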